- Are participating or participated within the last 12 months in PXE trials (eg, trials with PPi, PPi analogues such as bisphosphonate, or ENPP1 and its analogues) or in clinical trials relating to bone mineralization.
- Used bisphosphonate in the preceding 12 months or had plans to use bisphosphonate during the study.
- Used strong inhibitors or inducers of Cytochrome P450 isozymes, 2C19, 3A4, or 3A5.
- . 50
- Have an alkaline phosphatase < lower limit of normal (LLN) range.
- Have alanine aminotransferase or aspartate aminotransferase >2 × upper limit of normal (ULN) range; total bilirubin > 1× ULN.
- Have PLP > ULN.
- Have hemoglobin <10.0 g/dL.

- Have a QTcF interval duration >450 ms at screening.
- Have moderate to severe renal insufficiency (Creatinine clearance <60 mL/min by Cockcroft-Gault method).
- Are pregnant or breast-feeding women.
- Were women of childbearing potential unwilling to use contraceptive methods.
- Have a history of sulfonamide allergy.
- Have any elective surgery planned during the study period.
- Have any other significant condition (medical, psychiatric, social, or medication) that, in the judgment of the Investigator, would prevent full participation or would be inappropriate for the study.

Investigational Medicinal Product, Dose, and Mode of Administration

- Matching placebo tablets
- Tablets to be administered orally for once daily dosing.

Planned Sample Size and Key Statistical Analysis

CCI

Sample size is not

based on statistical consideration but is chosen on the basis of feasibility and clinical consideration from biomarker results of the completed Phase 1 healthy volunteer studies.

Safety endpoints, difference in biomarkers between active doses and placebo, plasma concentration of DS-1211a, and PK parameters will be summarized by descriptive statistics. Plasma concentration of DS-1211a will be also analyzed by noncompartmental methods. Observed values at each assessment and the absolute change and percentage change from baseline will be numerically summarized for primary and exploratory biomarkers by treatment group over time. The 95% confidence interval will be presented for percentage change from baseline in PPi and PLP.

TABLE OF CONTENTS

INVES	TIGATOR AGREEMENT	2
SUMM	ARY OF CHANGES	3
PROTO	OCOL SYNOPSIS	5
LIST O	F ABBREVIATIONS	15
1.	INTRODUCTION	17
1.1.	Background	17
1.2.	Study Rationale	17
2.	OBJECTIVES, OUTCOME MEASURES, AND ENDPOINTS	18
2.1.	Study Objectives	18
3.	STUDY DESIGN	20

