2.1. Study Objectives

The objectives, definitions of associated endpoints as well as applicable outcome measures are described in Table 2.1. Further requirements for the endpoint analyses and censoring rules, where applicable, can be found in Section 11.4 Section 11.5, and Section 11.6.

Study results, based on the analysis of below endpoints, will be analyzed to assess the dose for future clinical trials.

Table 2.1: Description of Objectives, Outcome Measures, and Endpoints

Objectives	Outcome Measure	Endpoints	Category				
Primary							
To assess the safety and tolerability of DS-1211b compared with placebo in subjects with PXE	Title: Safety parameters during the study Description: Descriptive statistics of safety endpoints Time frame: From the time the subject signs the study ICF and up to Day 98 (14 days after the last dose of study drugs)	Incidence of AEs, including SAEs, and treatment-emergent AEs, physical examination/assessment findings including vital sign measurements, standard clinical laboratory parameters, and ECGs	Safety				
To assess the dose response by assessing the treatment changes in PD endpoints	Title: PD endpoints Description: Profiles of ALP and TNAP substrates Time frame: Data are collected at baseline through Day 98.	ALP, PPi, and PLP	Pharmacodynamic				
Secondary							
To characterize the PK of DS-1211a (the free form of DS-1211b in plasma) in subjects with PXE Title: PK endpoints Description: Plasma concentration and PK parameters of DS-1211a Time frame: Data are collected at baseline through Day 84.		Plasma concentration and PK parameters of DS-1211a Include, but are not limited to, Cmax, Tmax, Ctrough, AUCtau, AUClast, and AUCinf (if possible to calculate)	Pharmacokinetic				

[figure not shown]

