3.2. Discussion of Study Design

This safety, tolerability, and dose-ranging study will evaluate DS-1211b doses that will inhibit TNAP sufficiently

Safety, tolerability, PK, and mechanism of action (MOA)-related PD biomarkers (ALP, PPi, and PLP) will be assessed from the doses, doses, of DS-1211b versus placebo. TNAP inhibition increases PPi levels, the MOA by which DS-1211b is proposed to reduce ectopic calcification. However, excessive TNAP inhibition increases the risk of recapitulating clinical manifestations of hypophosphatasia (HPP), a genetic mineralization disorder of TNAP deficiency accompanied by abnormally and persistently elevated PPi and PLP levels. Therefore, a careful benefit-to-risk characterization of the extent of TNAP inhibition that achieves a balance between increases in PPi versus increases in PLP is critical for selecting a target DS-1211b dose for later studies.

The 3 doses proposed for this study cover the likely range of a clinically safe and effective dose, based on results from nonclinical pharmacology studies, completed studies in healthy volunteers (safety, TNAP inhibition, PPi and PLP), published literature in HPP (PLP and PPi), and literature in PXE (PPi), as discussed in Section 1.

These results will be used for modeling and simulation at the end of the study to further evaluate the eventual recommended clinical dose for future clinical trials.

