11.5.3. Biomarker Analyses

All biomarker analyses will be based on Biomarker Analysis Set. Observed values at each assessment and the absolute change and percentage change from baseline will be numerically summarized for primary and exploratory biomarkers by treatment group over time. The 95% confidence interval will be presented for percentage change from baseline in ALP, PPi, and PLP. The baseline of biomarker data is defined as the last nonmissing assessment collected prior to the first dose of study medication.

Difference in primary and exploratory biomarkers between active doses and placebo will be summarized by descriptive statistics.

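### The primary dose-response objective has a stated 95% CI for change from baseline but none for each dose against placebo; Section 11.5.3 could add one at little cost.

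*Combined protocol and SAP*

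**What the plan says.** - **Objective.** Table 2.1 lists under Primary: "To assess the dose response by assessing the treatment changes in PD endpoints", with ALP, PPi and PLP as the endpoints. Section 2.1 adds that study results "will be analyzed to assess the dose for future clinical trials".
- **Comparison.** Section 3.2 says these markers are assessed at the doses "of DS-1211b versus placebo". It also says that characterising a level of enzyme inhibition which "achieves a balance between increases in PPi versus increases in PLP is critical for selecting a target DS-1211b dose for later studies".
- **Analysis.** Section 11.5.2 refers to Section 11.5.3. There, observed values, absolute change and percentage change are summarised by treatment group over time. Then: "The 95% confidence interval will be presented for percentage change from baseline in ALP, PPi, and PLP". The comparison with placebo has its own sentence: "Difference in primary and exploratory biomarkers between active doses and placebo will be summarized by descriptive statistics".
- **Meaning of descriptive statistics.** Section 11.1 gives the default for continuous variables: n, mean, SD, median, minimum and maximum. The longer list for PK in Section 11.5.1 has no interval either.
- **Synopsis.** The corresponding sentence under Planned Sample Size and Key Statistical Analysis names two markers, not three: "The 95% confidence interval will be presented for percentage change from baseline in PPi and PLP".
- **Other routes.** Section 3.2 says: "These results will be used for modeling and simulation at the end of the study". It names no model. Section 11.10 leaves the biomarker methods to a SAP to be finalised before database lock.

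**The concern.** The trial randomises 1:1:1:1 to three doses and placebo, so the comparison protected by randomisation is dose minus placebo. The stated interval belongs to a different quantity, change from baseline. Because its sentence follows the one on summaries by treatment group, it is most naturally read as one interval per arm.

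A within-arm interval carries any drift or regression to the mean that placebo subjects share, and it leaves out the sampling error of the placebo arm. Someone weighing PPi increases against PLP increases across doses would have intervals for the wrong quantity, and would see more precision than the placebo comparison has if the arms have similar SDs.

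**Working it through.** The documents give no planned precision to reproduce: Section 11.9 says the sample size is not statistically based, and no SD, effect size or correlation is stated. What follows is illustrative.

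**Inputs from the documents.** About 12 to 16 subjects per arm (synopsis, Study Design) and four arms at 1:1:1:1 (Section 3.1).

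**Assumptions.** SD ratios and baseline correlations as listed; complete data; roughly normal changes on an absolute or log scale. Half-widths are in units of the active arm's SD of change.

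**1. Within one arm:** t(0.975, n−1)/√n.
- n=12: 2.201/3.464 = 0.635
- n=16: 2.131/4 = 0.533

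**2. Dose minus placebo, equal SDs:** t(0.975, 2n−2)·√(2/n).
- n=12: 2.074 × 0.408 = 0.847, and 0.847/0.635 = 1.33
- n=16: 2.042 × 0.354 = 0.722, and 0.722/0.533 = 1.36 (1.355 before rounding)

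**3. Unequal SDs** (Welch), with r the placebo SD divided by the active SD: t(0.975, df)·√((1+r²)/n), where df = (n−1)(1+r²)²/(1+r⁴).

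| r | n=12 | ratio to within-arm | n=16 | ratio to within-arm |
|---|---|---|---|---|
| 0.5 | 0.684 | 1.08 | 0.580 | 1.09 |
| 1 | 0.847 | 1.33 | 0.722 | 1.36 |
| 2 | 1.367 | 2.15 | 1.159 | 2.18 |

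The ratio depends heavily on r, which the documents do not give.

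**4. Gain from baseline adjustment.** The unadjusted interval with variance pooled over four arms is t(0.975, 4n−4)·√(2/n), giving 0.823 (n=12) and 0.707 (n=16). ANCOVA, with equal baseline and follow-up variance and baseline correlation ρ, is t(0.975, 4n−5)·√(2/n)·√((1+ρ)/2).
- ρ=0.5: 0.713 and 0.613, about 13% narrower
- ρ=0.8: 0.781 and 0.671, about 5% narrower
- ρ=0.9: about 0.80 and 0.690, 2.5% narrower

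**5. Pooled or arm-specific variance.** This was simulated with 20,000 replicates, four arms, one follow-up time and a common slope; the arm-specific fit used weighted least squares with Satterthwaite degrees of freedom.
- Equal variances: arm-specific intervals are about 3% wider at n=12 (0.739 against 0.717 at ρ=0.5) and 2% wider at n=16 (0.628 against 0.616).
- Placebo residual SD twice that of the active arms (ρ=0.5): a pooled 95% interval covers about 90%.
- Placebo residual SD half that of the active arms (ρ=0.5): a pooled 95% interval covers about 97%.
- In both unequal cases, arm-specific variances bring coverage back to about 95%.

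**The case against.** The strongest reply is that the plan does what it promises. The objective is worded in terms of treatment changes; Section 11.5.3 reports changes by arm with intervals, plus differences from placebo; and the trial is openly feasibility-sized. Section 3.2 sends dose selection to modelling, and its worry about excessive TNAP inhibition also concerns levels within an arm. Most of this stands. A descriptive design is legitimate, no hypothesis test is promised, and the plan does not contradict itself on the placebo comparison. But it already reports intervals without testing, so an interval for the placebo contrast is the same kind of estimation. The modelling sentence is too unspecific to replace it.

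Second, the SAP may already contain the contrast, and Section 11.5.2 has a figure that could not be read. This stands as a limit. A reader might infer that the whole plan lacks a between-arm interval. The documents do not support that; they show only what Section 11.5.3 states. Nor does that section say that nothing else will be reported, and the Section 11.1 list is a default that can be overridden.

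Third, a reader can compute an unadjusted Welch interval from n, mean and SD. That is true. One might infer that its scale would necessarily be picked after the fact, but Section 11.5.3 already names absolute and percentage change. The adjusted interval's advantage over it is modest: against an average Welch half-width of about 0.84 at n=12, arm-specific ANCOVA gives 0.739, 0.808 and 0.831, which is about 12%, 4% and 1% narrower at ρ of 0.5, 0.8 and 0.9.

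Fourth, the choice of model needs care. Visit 5 is Day 84 or the day of early discontinuation (Table 3.1), so an analysis simply at Visit 5 may mix durations of exposure. A repeated-measures model with arm-specific unstructured covariance over three post-baseline visits needs 4 × 6 = 24 covariance parameters from 48 to 64 subjects, and the 2% to 3% cost above does not cover it. Both points stand and shape the fix.

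**Conclusion.** The point holds as an inexpensive improvement that should be made, not as an error. In Section 11.5.3 the stated 95% CI goes to change from baseline, while the randomised comparison behind a primary objective has no stated interval.

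With equal SDs the dose-minus-placebo interval is 33% (n=12) to 36% (n=16) wider than the arm's own, so within-arm intervals cannot stand in for it. All widths rest on assumed SDs and correlations. The main benefit is an interval for the right contrast; the gain in precision from adjustment is secondary.

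A reader might go further and conclude that the analysis is invalid or that a powered test is missing. The documents support neither, given the declared descriptive design. Confidence is medium because the SAP was not available.

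The mismatch between the synopsis (PPi and PLP) and Section 11.5.3 (ALP, PPi and PLP) is plain on the text, but editorial.

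**What to change.** In Section 11.5.3 and the SAP, before unblinding:

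1. State that for ALP, PPi and PLP each dose minus placebo will be estimated with a 95% CI, without hypothesis testing, from an ANCOVA adjusted for the baseline value already collected.
2. Name the predose timepoint and the scale, for example log values back-transformed to percentage change.
3. State how Visit 5 samples taken at early discontinuation enter the analysis.
4. Use a variance estimate that lets placebo and active arms differ.
5. Keep the within-arm summaries as supportive. A dose-trend contrast is optional. Do not adopt an MMRM with arm-specific covariance without first checking that it can be fitted at 12 to 16 per arm.
6. Make the synopsis and Section 11.5.3 agree on which markers receive a CI.

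If the SAP already specifies items 1 to 4, a cross-reference in Section 11.5.3 settles them.

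The cost is a few lines of text and one model per marker, with no new visits, samples, subjects or testing hierarchy. Allowing unequal variances costs about 2% to 3% in interval width if the arms turn out to have equal variance.

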11.5.4. Pharmacogenetic (Inherited Genetic) Analyses

11.6. Safety Analyses

Safety analysis will be performed by using the Safety Analysis Set and subjects will be analyzed according to their actual treatment received. The baseline value for clinical laboratory, vital sign, and ECG values is defined as the last nonmissing value prior to the first dose of study medication.

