3.3. Schedule of Events

Table 3.1: Schedule of Events

Period	Screening	Baseline	Tre	eatment	Period	Postdose	Follow-up	Notes
Visit Number	1	2	3	4	5 (EOT)	6	7	
Study Day	- 30 to -1	1	15	43	84ª	Last dose+3 ^{b,c}	98°	^a Or day of early discontinuation. ^b To be scheduled at 2 to 4 days after last dose (eg, Visit 5 or early discontinuation). ^c In-home visit unless otherwise specified by Investigator.
Window (days)			±3	±3	±3	±1	±5	
Eligibility Assessments								
Informed consent	X							Obtain prior to performing any study procedures
Inclusion/Exclusion	X							
Randomization		X						
Demographics	X							
History								
Medical/Surgical	X							
Safety Assessments								
Vital signs	х	Х	Х	X	Х	Х	X	Measurements include pulse, respiratory rate, body temperature, and systolic and diastolic blood pressure. Blood pressure to be recorded while subject is in recumbent position, having rested in this position for at least 5 minutes. Vital signs to be collected after ECGs and prior to blood draws
Height/Weight	X							
Physical examination	X	Х	X	X	X		X ^d	^d Physical assessment to be performed by visiting nurse for the in-home visit.

Period	Screening	Baseline	Tre	atment	Period	Postdose	Follow-up	Notes
Visit Number	1	2	3	4	5 (EOT)	6	7	
Study Day	- 30 to -1	1	15	43	84ª	Last dose+3 ^{b,c}	98°	^a Or day of early discontinuation. ^b To be scheduled at 2 to 4 days after last dose (eg, Visit 5 or early discontinuation). ^c In-home visit unless otherwise specified by Investigator.
Window (days)			±3	±3	±3	±1	±5	
Triplicate 12-lead ECG	X	х	х	X	X		X	 See Table 3.2 for detailed information on Visits 2 to 5. ECGs to be collected prior to vital signs and blood draws Triplicates at each collection Screening and follow-up visits (V1 and V7): 1 triplicate collection
AEs	X				X		All AEs occurring after the subject signs the ICF and up to Day 98 (14 days after last dose) should be collected.	
SAEs	Х				X		All SAEs occurring after the subject signs the ICF and up to Day 98 (14 days after last dose) should be collected.	
Medications and Nondrug Therapies								
Prior medications	Х							Medications used within 30 days prior to screening will be recorded. COVID-19 vaccination to be recorded regardless of time frame relative to screening.
Concomitant medications	X	X	X	X	X		X	
Laboratory Assessments								
Hematology	Х	Х	X	Х	Х		X	Fasting required. Blood collection should follow ECG and vital signs if indicated at same time point. See Section 9.8 for details

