4.2. Exclusion Criteria

Individuals who meet any of the following criteria at screening will be disqualified from entering the study:

- 1. Have a history of bone fracture in the past 6 months.
- 2. Have a history of active metabolic bone disease that significantly affect the interpretation of study biomarker results, excluding osteopenia or osteoporosis without fragility fracture.
- 3. Have a history of calcium pyrophosphate deposit disease such as chondrocalcinosis, pseudogout, and pyrophosphate arthropathy.
- 4. Have a history of hypophosphatasia.
- 5. Have a history of untreated hyperparathyroidism.
- 6. Participated in another interventional research study in the past 60 days.
- 7. Are participating or have participated within the last 12 months in PXE trials (eg, trials with PPi, PPi analogues such as bisphosphonate, or ENPP1 and its analogues) or in clinical trials relating to bone mineralization.

- 8. Used bisphosphonate in the preceding 12 months or had plans to use bisphosphonate during the study.
- 9. Used strong inhibitors or inducers of Cytochrome P450 isozymes, 2C19, 3A4, or 3A5 (Table 17.1 and Table 17.2)
- 10. CGI
- 12. Have an alkaline phosphatase < lower limit of normal (LLN) range
- 13. Have alanine aminotransferase (ALT) or aspartate aminotransferase (AST) >2 × upper limit of normal (ULN) range; total bilirubin >1 × ULN
- 14. Have PLP >ULN
- 15. Have hemoglobin <10.0 g/dL.
- 16. Have a QTcF interval duration >450 ms at screening.
- 17. Have moderate to severe renal insufficiency (Creatinine clearance <60 mL/min by Cockcroft-Gault method).
- 18. Are pregnant or breast-feeding women.
- 19. Are female participants unwilling to use contraceptive methods.
- 20. Have a history of sulfonamide allergy.
- 21. Have any elective surgery planned during the study period.
- 22. Have any other significant condition (medical, psychiatric, social, or medication) that, in the judgment of the Investigator, would prevent full participation or would be inappropriate for the study.

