9.10. Electrocardiograms

Twelve-lead ECGs in triplicate will be performed and recorded for every subject as per the SoE (Table 3.1). Vital signs will be collected after ECG measurements, and blood collection should occur after the vital signs (if indicated at the same timepoint).

The ECG will be measured after the subject has rested in a recumbent position for 5 minutes or more. Whether or not measurement is performed, on what date the measurement is performed, and what the results and findings are for the following parameters will be recorded: heart rate, PR interval, RR interval, QRS amplitude, and QT interval.

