11.6.4. Electrocardiogram Analyses

Descriptive statistics will be provided for the ECG measurements by scheduled time of evaluation and by treatment group for the safety population, as well as for the change from baseline. In addition, the number and percentage of subjects with ECG interval values meeting the criteria will be tabulated (eg, QTc \leq 450 ms, > 450 to \leq 480 ms, > 480 ms to \leq 500 ms, and > 500 ms). Data from ECG will also be presented in the data listings.

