11.10. Statistical Analysis Process

The clinical study will be analyzed by the Sponsor or its agent/CRO.

The SAP will provide the statistical methods and definitions for the analysis of the safety and biomarker data, as well as describe the approaches to be taken for summarizing other clinical study information such as subject disposition, demographic and baseline characteristics, study drug exposure, and prior and concomitant medications. The SAP will also include a description of how missing, unused, and spurious data will be addressed.

The SAP will be finalized prior to database lock to preserve the integrity of the statistical analysis and clinical study conclusions.

All statistical analyses will be performed by using SAS® Version 9.4 or higher (SAS Institute, Cary, NC 27513).

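### Does the plan need changing because it does not say how triplicate ECG readings are combined, and lists QRS amplitude but not QRS duration?

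*Combined protocol and SAP*

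**What the plan says.** The ECG row of Table 3.1 (Section 3.3) specifies "Triplicates at each collection", with one triplicate each at screening and follow-up, and refers the reader to Table 3.2 for Visits 2 to 5. Section 9.10 repeats that "Twelve-lead ECGs in triplicate will be performed and recorded for every subject" and adds that "what the results and findings are for the following parameters will be recorded: heart rate, PR interval, RR interval, QRS amplitude, and QT interval".

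For analysis, Section 11.6 gives one baseline rule for three kinds of data: "The baseline value for clinical laboratory, vital sign, and ECG values is defined as the last nonmissing value prior to the first dose". Section 11.6.4 plans descriptive statistics by scheduled time and for change from baseline. It also says that "the number and percentage of subjects with ECG interval values meeting the criteria will be tabulated", offering QTc cuts at 450, 480 and 500 ms as examples, and that "Data from ECG will also be presented in the data listings". It names no correction formula. Exclusion criterion 16 in Section 4.2 does name one: "Have a QTcF interval duration >450 ms at screening".

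Section 11.10 states that "The SAP will provide the statistical methods and definitions for the analysis of the safety and biomarker data", and that the SAP is to be final before database lock.

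**The concern.** With three readings at each time point, the ECG value there is undefined until someone says how they are reduced to one. A baseline rule written for single laboratory or vital-sign values can be taken literally as the last of the three readings, which discards two thirds of the data. It can also be taken as the average of the last triplicate. The same question arises for post-dose values, for the QTc categories and for the screening criterion.

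Safety is a primary objective and ECG is a named safety endpoint. Arms hold about 12 to 16 subjects, so one subject moving between QTc categories shifts a percentage by 1/16 = 6 to 1/12 = 8 points. A rule chosen after seeing the data would be unwelcome.

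The QRS entry raised a separate worry. An analysis definition can be written later, but a measurement never captured cannot be supplied by a SAP. QTcF follows from the recorded QT and RR intervals. QRS duration does not follow from anything on the Section 9.10 list.

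**Working it through.** The plan gives no figure to reproduce: Section 11.9 says the sample size has no statistical basis, and no QTc variability is reported. The check therefore compares the texts and then sizes the effect under stated assumptions.

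**1. Where a rule could sit.** Section 11.10 assigns safety definitions to the SAP. Table 3.1 sends ECG detail for Visits 2 to 5, including the baseline visit, to Table 3.2. That table is in the list of tables, but its content is not in the text available here, and neither is a separate SAP text. Absence from the available text does not show absence from the plan.

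**2. How the baseline sentence reads.** Table 3.1 treats the triplicate as the unit of collection. On that footing, the latest value before dosing is the value of the last triplicate. The single-reading interpretation is possible but not the more natural one.

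**3. Effect on mean change.** Model each reading as the true value at that time, plus an occasion error (SD so), plus a replicate error (SD sr), both with mean zero. One reading and the mean of three then have the same expectation, so the expected change from baseline is identical whether neither, one or both time points are averaged.

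**4. Effect on the SD of change.** Assumed so = 8 ms and sr = 6, 8 or 10 ms.

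| Rule | Variance | sr = 6 | sr = 8 | sr = 10 |
|---|---|---|---|---|
| Single reading at both times | 2(so² + sr²) | 200, SD 14.1 | 256, SD 16.0 | 328, SD 18.1 |
| Only post-dose averaged | 2so² + sr² + sr²/3 | 176, SD 13.3 | 213.3, SD 14.6 | 261.3, SD 16.2 |
| Both averaged | 2(so² + sr²/3) | 152, SD 12.3 | 170.7, SD 13.1 | 194.7, SD 14.0 |

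Averaging both rather than neither cuts the variance by 1 − 152/200 = 24%, 1 − 170.7/256 = 33% and 1 − 194.7/328 = 41%. These percentages depend on the ratio of sr to so:

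- so = 8, sr = 3: 1 − 134/146 = 8%.
- so = 8, sr = 4: 1 − 138.7/160 = 13%.
- so = 5, sr = 10: 1 − 116.7/250 = 53%.

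The documents do not say where in this range the trial lies.

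**5. Effect on a category.** Take a subject whose usual QTcF is 440 ms, with so = 8 and sr = 6, 8 or 10. The chance of exceeding 450 ms at one time point is:

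- Triplicate mean, 1 − Φ(10/√(so² + sr²/3)): 13%, 14%, 16%.
- One reading, 1 − Φ(10/√(so² + sr²)): 16%, 19%, 22%.
- Any of three readings, ∫φ(z){1 − Φ((10 − so·z)/sr)³}dz: 29%, 37%, 44%.

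The two plausible readings of the text differ by about 3 to 6 percentage points for a subject placed 10 ms below the cut. The large contrast needs the third rule, which nothing in the documents suggests.

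**6. QRS.** Section 9.10 says results for the listed parameters are recorded. It does not say that nothing else is. QTcF is not listed either, yet eligibility depends on it. The ECGs themselves are recorded, and Section 12.4 requires source records to be kept. Section 11.6.4 names QTc and plans no analysis of QRS by name.

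**The case for a change.** The strongest case for acting is that the protocol did not simply stay silent. It wrote a baseline rule, and that rule is ambiguous for triplicates. Nor can the SAP reach everything: the screening criterion is applied before randomization, and a field missing from the eCRF cannot be added at analysis. Stating the rule would cost a few words and one averaging step on data already collected, and would remove any choice after unblinding.

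Some of this stands. The ambiguity is real, and averaging is the more precise use of the data whatever the SDs, provided replicate error is above zero. The direction of the calculations is therefore not in doubt, only their size. It is also true that the SAP does not govern eligibility. But eligibility is settled before allocation, so whichever way a site reads the screening triplicate, the choice applies alike to subjects who later enter each arm and does not bias the comparison between arms.

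The choice-after-unblinding point is met by Section 11.10, which requires the SAP before database lock. The formula point is slight, because QTcF is the only correction the protocol names. The fear that averaging, or its absence, would hide an extreme reading is eased by the planned ECG listings, which can carry individual replicates.

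The data-capture argument is weaker than it first appears. It needs Section 9.10 to be an exclusive list and the stored tracings to be unusable. The documents establish neither, and the eCRF is not available to check.

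**Conclusion.** The observation is accurate, but no change to the plan follows. The replicate rule is an ordinary definition that the protocol assigns to the SAP, and averaging the available readings, with QTc taken as QTcF, is what an analyst would do. If single readings were used instead, the mean change would be unaffected in expectation. The cost would be a wider SD, by roughly 2 to 4 ms (14.1 against 12.3 up to 18.1 against 14.0), in a descriptive table with no planned test, no ECG confidence interval and no interim decision resting on it. Those figures rest on assumed SDs and independent replicate errors, and outside the assumed values the variance saving could be as little as 8% or as much as 53%.

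QRS amplitude is probably a slip for QRS duration, though the documents do not settle it. It is a wording query for the sponsor, and no stated result depends on it. The conclusion would be different only if Table 3.2 or the SAP laid down a rule that treats baseline and post-dose readings unequally, such as taking the highest post-dose replicate. Nothing in the available text points that way.
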